*Hypothesis (see Figure 2): Enrollees with asthma in HSA-HDHPs without PDLs will have worse adherence to controller medications, greater need for rescue medications, and higher rates of asthma-related ED visits and hospitalizations, with widening of income and racial/ethnic disparities; the addition of a PDL will improve use of controllers and rescue medications, reduce ED and hospitalization rates, and lessen disparities.*

Analyses will compare changes in outcomes from baseline to up to three years of follow-up among 1) asthma patients switched to HSA-HDHPs without PDLs from traditional plans vs. matched patients whose employers remain in traditional plans; and 2) patients switched to HSA-HDHPs with PDLs from traditional plans vs. matched controls remaining in HSA-HDHPs without PDLs. Sensitivity analyses will compare patients switched to HSA-HDHPs with PDLs from traditional plans vs. those who remain in traditional plans to examine the combined impact of both increasing the deductible and gaining a PDL. We will use separate regression models to compare year-to-year changes for each intervention group relative to its matched control group, rather than including all patients in a single model with multiple interaction terms. For secondary analyses of enrollees in the larger set of plan types that include PDLs, we will compare enrollees who are switched from plans with no PDL to plans with a PDL vs. those who remain in plans without a PDL. These analyses will match and adjust for different baseline plan types and deductible levels.

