In all statistical models, we will include key individual-level predictors from Table 2 to adjust for potential confounding. To determine the impact of HSA-HDHP with and without PDLs on vulnerable populations (RQ-4) and test for heterogeneity of treatment effects among vulnerable populations (HT-1-4), we will first perform stratified analyses, comparing outcomes between intervention and control subgroups defined by the binary measures of the risk factors of interest (low income, minority race/ethnicity, moderate-severe asthma, presence of other chronic conditions (including co-morbid diagnosis of COPD; we will also conduct analyses limited to ages 4-50 to remove the effect of COPD co-morbid diagnoses), high ACG morbidity). We hypothesize that these vulnerable subgroups will have worse adherence, more frequent adverse clinical outcomes, and higher OOP costs. We will use three-way interaction terms (insurance type \* study period \* subgroup) to test for statistical differences between subgroups in the impact of the change to an HSA-HDHP with PDL vs. remaining in a traditional plan. Heterogeneity of treatment effect analyses for these key variables will be reported along with overall findings from the combined population. Given that we will be conducting sub-group analyses to test for heterogeneity of treatment effect based on race/ethnicity and income using three-way interaction terms, we elected to separate the analyses of heterogeneity of treatment effect by age group into Aim 3 (described below), rather than add a fourth interaction term to the analyses in Aim 2. In Aim 2 analyses, we will include

both adults and children together, with age included as a co-variate. Given that health plan cost-sharing policies in HSA-HDHPs and PDLs usually apply across enrollees regardless of age, and given that health plans, employers, policy makers, and families must make decisions about HSA-HDHPs and PDLs for both adults and children together, we felt it was important to evaluate the impact at the overall population level.

**Aim 3:** to examine the extent to which the response to HSA-HDHPs and PDLs is affected by the presence of other family members with asthma or other chronic conditions.

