***Hypothesis:** Adults with asthma will disproportionately experience negative effects of HSA-HDHPs on adherence and outcomes relative to children with asthma (HT-2), as will patients who have other family members with asthma or other chronic conditions; differences will be mitigated by the addition of a PDL.*

Aim 3 will focus on intra-familial trade-offs in response to cost-sharing changes in HSA-HDHPs and PDLs, and on adult-child differences in response to HSA-HDHPs and PDLs. Analyses will use the same population, outcomes, study group comparisons, and modeling strategies as Aims 1 and 2 except that we will perform stratified analyses, comparing outcomes between intervention and control groups stratified by adult/child status (RQ-4). To statistically test for heterogeneity of treatment effect for adults vs. children (HT-1-3), we will use three-way interaction terms (insurance type \* study period \* adult/child) to test for statistical differences between adults and children in the impact of the change to an HSA-HDHP with PDL vs. remaining in an HSA-HDHP without PDL, and the change to an HSA-HDHP without PDL vs. remaining in a traditional plan. Analyses will be done at the individual level, but will include family-level variables listed in Table 2 as predictors of interest. Separately for adults and children, we will test the extent to which having another family member with asthma, another chronic condition, or high baseline family ACG morbidity modifies the impact of HDHPs and PDLs on study outcomes for an individual asthma patient. The primary predictor of interest will be the interaction between the family-level variable, study period, and study group.

We will conduct secondary analyses on the subset of families in the study population that have both an adult and child with asthma insured in the same family plan, and will assess whether adults and children within the same family are differentially impacted by HDHPs and PDLs by comparing outcomes between intervention and control groups in separate strata for adults and children (HT- 1-2, IR-5).

**Aim 4:** to examine the impact of HSA-HDHPs with and without PDLs on out-of-pocket (OOP) costs for patients with asthma.

***Hypothesis:** Enrollees with asthma in HSA-HDHPs without PDLs will have higher OOP costs and increased financial burden as measured by the percent of income spent on OOP costs; the addition of a PDL will diminish these adverse outcomes.*

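### The one contrast named for Aim 2's vulnerable-subgroup interaction is the combined switch from a traditional plan to an HSA-HDHP with PDL, which cannot separate the widening and lessening hypotheses

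*Combined protocol and SAP*

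**What the plan says.** The Aim 2 hypothesis (Analysis plan) has two disparity parts of opposite direction. Enrollees in HSA-HDHPs without PDLs are expected to do worse, "with widening of income and racial/ethnic disparities; the addition of a PDL will improve use of controllers and rescue medications"; the PDL is also expected to "reduce ED and hospitalization rates, and lessen disparities".

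Two main comparisons follow. The first is "asthma patients switched to HSA-HDHPs without PDLs from traditional plans vs. matched patients whose employers remain in traditional plans". The second is worded as "patients switched to HSA-HDHPs with PDLs from traditional plans vs. matched controls remaining in HSA-HDHPs without PDLs". A third is given lower rank: "Sensitivity analyses will compare patients switched to HSA-HDHPs with PDLs from traditional plans vs. those who remain in traditional plans", with the stated purpose of showing the joint effect of a higher deductible and a new PDL. The Study Population section likewise lists the group moving from a traditional plan to an HSA-HDHP with PDL under secondary analyses.

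For vulnerable subgroups, Aim 2 plans stratified analyses and then three-way interactions (subgroup by period by plan type). The task given to these interactions is as follows: "test for statistical differences between subgroups in the impact of the change to an HSA-HDHP with PDL vs. remaining in a traditional plan". A later sentence mentions interactions for race/ethnicity and income but names no contrast; its purpose is to explain why age was moved to Aim 3.

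Aim 3 specifies its adult/child interaction for both single steps: "in the impact of the change to an HSA-HDHP with PDL vs. remaining in an HSA-HDHP without PDL", and the move to an HSA-HDHP without PDL against staying in a traditional plan.

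**The concern.** Each disparity hypothesis concerns one step: the deductible step (traditional plan to HSA-HDHP without PDL) or the PDL step (HSA-HDHP without PDL to with PDL). The contrast named for the interaction spans both steps at once. If followed as written, the formal test would address whether vulnerable patients respond differently to the whole package, and neither hypothesis would have a named test. A null result could mean no disparity effect, or two real effects that offset. A non-null result could not be credited to either step.

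The heterogeneity results are to be reported with the overall findings, so the ambiguity would reach the main report. Aim 4 says its analyses resemble those of Aim 2, so the same contrast could carry over to out-of-pocket costs.

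**Working it through.** **Setting the sections side by side**

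| Place | Traditional → without PDL, vs stay traditional | Without PDL → with PDL, vs stay without PDL | Traditional → with PDL, vs stay traditional |
|---|---|---|---|
| Overview of Study Protocol | primary | primary | not listed as primary |
| Study Population | yes | yes | secondary |
| Aim 2 comparisons | main | main, but switchers said to come from traditional plans | sensitivity |
| Aim 2 subgroup interaction | not named | not named | **named** |
| Aim 3 adult/child interaction | named | named | not named |

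Aim 2 also specifies separate regression models for each intervention group against its own controls, so no pooled model would recover the components.

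**What the named interaction estimates**

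Let D1 be the difference (vulnerable minus other patients) in the difference-in-differences effect of the deductible step, and D2 the same for the PDL step. On the linear scale (log scale for ratio models), and with comparable populations:

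combined interaction = D1 + D2.

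For adherence (PDC), the hypotheses are D1 < 0 and D2 > 0. Illustrations, with values not in the documents: −4 + 4 = 0; −4 + 3 = −1; −4 + 2 = −2; −4 + 0 = −4. Conversely, an observed −2 fits (−2, 0) and (−4, +2) equally well.

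The nearest documented figures are main effects (Hypothesized Effect Size section): PDC down 5–9%, fills up 1–4%. Treating fills as if they were PDC, the sums run from −9 + 1 = −8 to −5 + 4 = −1, which is partial offset only.

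**The plan's own power figure**

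Table 3 gives 2.0% as the detectable PDC difference for 4,222 vs 16,888 (80% power, alpha 0.05, baseline 46%). A two-proportion calculation from these inputs gives 2.4% two-sided or 2.1% one-sided, so 2.0% is not reproduced. The two-means formula gives the SD that would yield it, two-sided:

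SD = 0.020 / [(1.960 + 0.842) × √(1/4,222 + 1/16,888)] = 0.020 / (2.802 × 0.01721) ≈ 0.415.

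A pre/post correlation near 0.65 would produce this SD, so it is an unstated input and not a demonstrated error. Table 3 has no row for the combined contrast or for any income or race/ethnicity interaction.

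**Detectable interactions on the single-step contrasts**

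For a subgroup with share f in both arms, the detectable interaction is the detectable main difference divided by √(f(1−f)). The shares are assumed.

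- PDL step (4,222 vs 16,888): 2.0 / √(0.25 × 0.75) = 4.6 points at f = 25%; 2.0 / 0.5 = 4.0 at f = 50%.
- Deductible step (18,000 vs 72,000), same SD: the main difference is 2.802 × 0.415 × √(1/18,000 + 1/72,000) ≈ 0.97 points, giving 2.2 and 1.9.

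**Power under illustrative scenarios** (f from 25% to 50%; the combined cohort's size is not given and is assumed here to be 4,222 with four controls each)

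| D1, D2 (points) | Deductible-step test | PDL-step test | Combined test |
|---|---|---|---|
| −4, +4 | above 99% | 68–80% | 5% (alpha) |
| −4, +3 | above 99% | 44–56% | 9–11% |
| −4, +2 | above 99% | 23–29% | 23–29% |
| −4, 0 | above 99% | 5% (alpha) | 68–80% |

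In the first row a larger cohort does not help, because the quantity tested is zero.

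**The case against.** Several points on the other side are fair.

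- **It is probably a slip.** The Aim 2 wording looks like the Aim 3 sentence with its middle missing. The Aim 2 subgroup paragraph opens by covering plans with and without PDLs, and Aim 3 says it follows the earlier aims' comparisons and modelling. This stands: the documents do not show a deliberate choice of the combined contrast. It is nevertheless the operative text.
- **Other subgroup evidence is planned.** A reader might infer that this is the only formal disparity test, or that the vulnerable-subgroup part of Aim 2 goes unanswered. Neither follows. Stratified estimates are planned, and a second sentence mentions race/ethnicity and income interactions without tying them to a contrast. What is missing is a named between-subgroup test on either primary contrast.
- **Cancellation is not a given.** A reader might infer that the test can show only a small residual. The documents give no subgroup effect sizes, and full offset is one scenario. If the PDL had no disparity effect, the combined test would pick up the widening alone, though it could not identify it as such. Exact additivity also assumes comparable populations, whereas the cohorts come from different switching employers.
- **The combined contrast has its own use.** Whether vulnerable patients fare differently under an HSA-HDHP with PDL than under traditional coverage is a legitimate question, and the Description of Comparators admits switchers from traditional plans. It is a different question from the two hypothesised.

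**Conclusion.** The point holds as an internal inconsistency that makes the interaction rule wrong as written. The only contrast named for Aim 2's vulnerable-subgroup interaction is one the plan elsewhere ranks as sensitivity or secondary, and its result cannot be attributed to the widening or the lessening hypothesis.

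The attribution problem needs no power calculation. It rests on additivity on the model scale and on comparable populations. How far the two steps offset is unknown. The power figures rest on the SD implied by Table 3, assumed subgroup shares of 25–50%, assumed interaction sizes, an assumed combined cohort size, and no allowance for clustering.

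**What to change.** 1. In the Aim 2 heterogeneity paragraph, specify the three-way interaction separately for (a) HSA-HDHP without PDL to with PDL against remaining without PDL, and (b) traditional plan to HSA-HDHP without PDL against remaining in a traditional plan. Keep the traditional-to-PDL interaction as a sensitivity analysis.
2. Reconcile the wording of Aim 2's second comparison, whose switchers come from traditional plans, with the Overview of Study Protocol and Study Population sections, where they start in an HSA-HDHP without PDL. The lessening test is not properly defined until this is done.
3. State the limited power for the PDL-step interaction: about 4.0 to 4.6 PDC points under the assumptions above. That is at or above the top of the 1–4% hypothesised for the whole PDL effect, although that figure is for fills.

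The cost is a few sentences of text and some extra model runs on cohorts that are already planned.

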Using methods from our prior family-level studies, we will aggregate individual member data to create family-level co-variates that will be applied to each subject and used for individual-level propensity matching and analyses. Patients with individual coverage will be considered a family of one. Family-level variables include: number of family members; mean age of children in the family; mean age of adults; baseline mean family ACG score; number of family members with asthma; and number of asthma and other medications used by the family, and number of ED visits and hospitalizations in the baseline year.

Our study population includes health plan members working for employers that either switched to an HSA-HDHP without PDL or HSA-HDHP with PDL, or remained in a traditional plan or an HSA-HDHP without PDL, respectively, for all employees. While this minimizes member-level selection, employer-level selection could still bias results. We will therefore use a validated and rigorous employer- and individual-level propensity score classification/matching approach (CI-1, 4-5) that is superior to a single-level matching technique. For employer-level propensity matching, potential predictors of an employer HSA-HDHP switch in our propensity score models will include employer size

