**Table 2: Predictors and covariates**

| Covariate                         | Use*    | Notes  |
|-----------------------------------|---------|--|
| Study period                      | P       | Pre (1 yr pre), Follow-up (up to 3 yrs post)   |
| Insurance type                    | P       | HSA-HDHP without PDL, HSA-HDHP with PDL, traditional plan  |
| Income                            | P, M, S | Subscriber income in dollars and as a % of Federal Poverty Level (FPL) (<250%, 250-399%, >400%)  |
| Lives in neighborhood with:       |         |  |
| Low education                     | P, M    | ≥25% with less than high school education  |
| High poverty                      | P, M    | ≥10% living below poverty level  |
| Low SES                           | P, M    | Either low education or high poverty   |
| Race/ethnicity                    | P, M, S | Hispanic; Asian; Black; White; Other   |
| Persistent asthma                 | P, S    | Based on HEDIS definition  |
| Severe asthma                     | P, S    | On oral steroids or omalizumab   |
| ACG Score                         | P, M, S | For patient and mean for family; >2 signifies high morbidity                                     |
| Other chronic conditions          | P, M, S | For patient, other family members, from AHRQ Chronic Condition Indicator list                    |
| Region of residence               | M       | State classified into 9 geographic regions   |
| Sex                               | P, M    |  |
| Age on index date                 | M       | For patient; mean for adults and children in family  |
| Adult vs. child                   | P, S    | Age 18-64 vs. age 4-17   |
| Family coverage                   | M       | In a family vs. individual plan  |
| Family size                       | M       | Number sharing same insurance account  |
| Family members with asthma        | P       | Other adults, other children   |
| Number of medications             | P, M    | For baseline year, controller, rescue, other (on and off PDL); for patient, other family members |
| Outpatient visits                 | M       | For baseline year: for patient and mean for family   |
| Hospitalization                   | M       | For baseline year: ≥1 admission, mean per family   |
| Total expenditures                | M       | For baseline year: for patient and mean for family   |
| Employer size                     | M       | 2-50; 51-250; 251-999; ≥1000 employees   |

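### One Aim 3 effect modifier, high family ACG morbidity, is a family mean that is not defined to exclude the index patient, so it mixes the patient's own morbidity with that of other members

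*Combined protocol and SAP*

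**What the plan says.** The protocol states Aim 3 as the extent to which the response to the plan designs is "affected by the presence of other family members with asthma or other chronic conditions". The Aim 3 text in the Analysis plan names three family modifiers: another member with asthma, another member's chronic condition, and a third, whether "high baseline family ACG morbidity modifies the impact of HDHPs and PDLs on study outcomes for an individual asthma patient". Each is tested through a three-way interaction of the family variable, study period and study group.

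Predictors and Covariates explains how family variables arise: "we will aggregate individual member data to create family-level co-variates that will be applied to each subject". It adds that "Patients with individual coverage will be considered a family of one" and lists "baseline mean family ACG score" among the results. Table 2 describes ACG as "For patient and mean for family; >2 signifies high morbidity". In the same table, family members with asthma are "Other adults, other children", and chronic conditions are "For patient, other family members, from AHRQ Chronic Condition Indicator list".

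Under Aim 2, high ACG morbidity of the patient is one of the subgroups tested for heterogeneity by a three-way interaction. Individual-level predictors from Table 2 enter all models to control confounding.

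**The concern.** Aim 3 is about pressure that arises from other people in the family. A modifier that contains the index patient's own score can be high because the patient is sick while the relatives are well, or low because the patient is well while a relative is sick.

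The plan itself expects sicker patients to respond differently. If they do, some of that difference will appear in the family-ACG interaction, and a positive result could be reported as an intra-familial trade-off when part of it is not. True burden from other members is also misclassified near the cut-off, which weakens the test for the effect of interest.

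The planned adjustment does not remove this. Entering the patient's ACG as a covariate, or matching on it, deals with differences in outcome level between groups. It does not take out a difference in the effect of the plan switch by patient morbidity. That needs the patient's ACG by period by study group term, which is not stated for Aim 3.

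**Working it through.** The documents give no power or precision figure for this interaction, so there is nothing of the plan's to reproduce. The check has two parts: what the text implies, and how much the patient contributes.

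**1. Is the patient in the mean?** This is not stated outright. Three things point to yes:
- Member data are aggregated by family and the result is then applied to each subject, with no exclusion mentioned.
- Individual coverage counts as a family of one, and its mean can only be the patient's own score.
- Table 2 names other members in the asthma, chronic-condition and medication rows, but not in the ACG row.

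**2. Weight and correlation.** Let M be the mean over k members, including the patient. The patient's weight is 1/k. The documents give no ACG variances or within-family correlations, so I assume equal variances and a within-family correlation r of 0.1 to 0.3.
- Own score with M: √[(1+(k−1)r)/k]
- Mean of the others with M: √[(k−1)(1+(k−1)r) / (k(1+(k−2)r))]
- Own score with mean of the others: r·√[(k−1)/(1+(k−2)r)]

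For k=4 and r=0.1 these are √(1.3/4)=0.57, √(3.9/4.8)=0.90 and 0.1·√(3/1.2)=0.16.

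| k | Patient's weight | Own vs M | Others vs M | Own vs others |
|---|---|---|---|---|
| 1 | 100% | 1.00 | none | none |
| 2 | 50% | 0.74–0.81 | 0.74–0.81 | 0.10–0.30 |
| 3 | 33% | 0.63–0.73 | 0.85–0.91 | 0.13–0.37 |
| 4 | 25% | 0.57–0.69 | 0.90–0.94 | 0.16–0.41 |

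At two members M follows both components equally. From three it follows the others more closely, but its correlation with the patient's own score is still well above that of the others-only mean (last column). That last column is not zero either, so leaving the patient out is not sufficient without the patient's own interaction term.

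**3. Sensitivity to the variance assumption.** Suppose the patient's SD is twice that of relatives and r=0. For k=2, Var(M)=(4+1)/4=1.25. Own vs M is 2/(2·√1.25)=0.89, and others vs M is 0.5/√1.25=0.45. The same calculation gives 0.82 vs 0.58 at k=3 and 0.76 vs 0.65 at k=4. With r=0.3 the pairs are 0.92 vs 0.64, 0.87 vs 0.79 and 0.82 vs 0.86.

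**4. Effect at the cut-off of 2.**
- If every other member scores 1, then (x+(k−1))/k > 2 when x > k+1. The patient alone makes the family high above 3 at k=2 and above 5 at k=4. At k=1 the family flag is the patient's own flag.
- Patient 4.0, partner 0.5: (4.0+0.5)/2=2.25, flagged with a well partner.
- Patient 1.0, partner 2.8: (1.0+2.8)/2=1.90, not flagged with a sick partner.

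**The case against.** A reader might infer that this modifier, or Aim 3 as a whole, measures the patient's own morbidity instead of the family's. The documents do not support that.
- The modifier equals the patient's score only for a family of one. Under equal variances the others dominate from three members up.
- It is one of three family modifiers and appears in neither the aim statement nor the hypothesis. The other two are described in terms of other members, and the adult/child contrast does not use it.

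It can also be said that inclusion of the patient is only inferred. The human-subjects section (Human Subjects Involvement, Characteristics, and Design) says that other members' data will be used in Aim 3 to create family variables, among them family-level morbidity. That falls short of excluding the patient, since the same list includes the number of family members.

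A whole-family measure has a rationale too. The conceptual model has the patient's out-of-pocket costs feeding the family's total burden, and the Background describes family deductibles. Total family morbidity is a fair question, but it differs from burden due to other members.

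Finally, own-ACG heterogeneity will be reported in Aim 2, so readers could compare the two results. Comparing separate models does not separate the two effects. What stands is that the defect is confined to one modifier and is a mixture. The lack of a stated exclusion and of an own-ACG interaction term remains.

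**Conclusion.** The concern holds for this one modifier. As written, and on the natural reading, high family ACG morbidity combines the patient's own score with that of relatives: 100% own for families of one, 50% for two, 33% for three and 25% for four. With equal variances and r of 0.1 to 0.3, its correlation with the patient's own score is 0.74–0.81 at two members and 0.57–0.69 at four, against 0.10–0.30 and 0.16–0.41 for a mean over the others only.

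A positive interaction could therefore partly reflect the patient's own morbidity. The documents do not allow one to say that it mostly would: the distribution of family size, the ACG variances and the within-family correlation are not given, and the balance shifts towards the patient if patients' scores vary more than relatives'. If the intention is already to exclude the patient, the text needs to say so. The change should be made before the analysis is run. Other Aim 3 results are not affected.

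**What to change.** For this modifier only:
- Define it as the baseline mean ACG of the other insured family members, with the same cut-off of 2.
- Put the patient's own ACG by period by study group term in the same model.
- Either run the test among patients with at least one other insured member, or code single coverage as a separate category, and state which.
- Keep the all-member mean for matching and, if wanted, as a sensitivity analysis of total family burden.

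This takes one derived variable and one additional model term, with its lower-order terms, and no new data. No stated sample size or power figure changes. The real cost is that single-coverage patients do not contribute to this test, with some loss of precision and a narrower population. Section B (Significance) puts more than 60% of HDHP enrollees in family plans, so up to about 100−60=40% could be affected if that background figure applied here. It does not describe this cohort. The loss would probably fall on the adult stratum, since children on employer coverage normally share a parent's plan (my inference).

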| Employer health care expenditures | M       | Per capita, for baseline year  |

\* P=predictors; M=used in propensity matching; S=used to stratify analyses

category; baseline level and trend of total per capita health care expenditure quintile; baseline level and trend of outpatient, ED, and hospital visits quintile; median employee age; median employee ACG score; and percentage of employees who are women, in family plans, and living in lower SES neighborhoods (Table 2). We will perform this employer-level match separately for each intervention group of interest (HSA-HDHPs with and without PDLs) in order to generate each comparison with the control group remaining in traditional plans or HSA-HDHPs without PDLs.

Intervention and control groups will be matched based on their baseline characteristics when both were in the same type of plan. We will set  $p < 0.05$  as a cutoff for including predictors and use backwards selection to choose a parsimonious model, testing for significant effects on remaining predictors when one is eliminated. Following methods in our ongoing work, we will stratify employers based on resulting propensity scores into quartiles. We will then perform individual-level propensity matching within each quartile (below) to develop a multiple control groups for each intervention group.

Within employer propensity quartiles, we will create closely matched control groups using individual-level propensity score matching (CI-1, 4-5), with family-level covariates included in the matching. Using individual and family-level covariates from the baseline period, we will match four contemporaneous control group patients to each intervention group patient within a standard propensity score caliper (0.2 of the standard deviation of the logit of the pooled baseline propensity score). Use of a comparison group matched at both employer- and individual-level will generate study cohorts with nearly identical employer/member demographics and baseline health care trends, offering a further degree of control for any potential changes that may influence specific study outcomes.

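### The secondary analysis of families with both an adult and a child with asthma asks whether the two are affected differently, but plans only separate adult and child comparisons and does not say that the adult-child difference will be estimated or tested in that subset.

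*Combined protocol and SAP*

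**What the plan says.** The analysis is described in the last paragraph of Aim 3 in the Analysis plan. It is restricted to "the subset of families in the study population that have both an adult and child with asthma insured in the same family plan". The plan states that it "will assess whether adults and children within the same family are differentially impacted by HDHPs and PDLs", and the method follows in the same sentence: "comparing outcomes between intervention and control groups in separate strata for adults and children". The sentence names no interaction, contrast or paired comparison.

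The paragraph before it, on the full Aim 3 population, is more complete. It stratifies by adult/child status and then adds a three-way term (insurance type by study period by adult/child) "to test for statistical differences between adults and children in the impact of the change to an HSA-HDHP with PDL", and likewise for the change to an HSA-HDHP without PDL. It also says "Analyses will use the same population, outcomes, study group comparisons, and modeling strategies as Aims 1 and 2" and "Analyses will be done at the individual level".

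Under Predictors and Covariates, the individual-level match is described as "we will match four contemporaneous control group patients to each intervention group patient". Family-level covariates enter that match, but families are not matched as units. No separate matching is described for the dual-asthma families, and neither their expected number nor the power for this analysis is given.

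**The concern.** Whether two groups are affected differently is a question about one quantity: the adult plan effect minus the child plan effect. Two separate intervention-control comparisons do not deliver that quantity. Readers will be left to compare two estimates or two p-values.

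The risk is practical. The Aim 3 hypothesis is that adults with asthma bear more of the harm. A result that is significant in adults and not in children would readily be taken as confirmation, and as evidence that families protect their children's care. The same pattern arises often by chance when the effects are identical.

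This is also the only planned adult-child comparison confined to families in which both have asthma and share a plan, and so a deductible and a household budget. The full-population interaction does not hold the family constant in that way. Leaving the difference unestimated here wastes the feature that makes the subset worth analysing.

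**Working it through.** **Plan's own figure.** There is none to reproduce. Table 3 covers overall and child-stratum contrasts, not the dual-asthma families or any adult-child difference.

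**1. The wording, side by side**

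| Analysis | Separate strata | Test of the difference |
|---|---|---|
| Aim 2, vulnerable subgroups | Yes, as a first step | Yes, three-way interaction |
| Aim 3, full population, adult vs child | Yes | Yes, three-way interaction |
| Aim 3, families with both an adult and a child with asthma | Yes | None stated |

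Elsewhere the plan treats stratifying and testing as two steps. Here only the first is written down.

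**2. How often equal effects look unequal.** Let each stratum have power p and let the true effects be equal. With independent estimates, the chance that exactly one stratum is significant is 2p(1 − p).

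- p = 0.80 (the power assumed under Sample Size and Power): 2 × 0.80 × 0.20 = 0.32.
- p = 0.50: 2 × 0.50 × 0.50 = 0.50.
- p = 0.30: 2 × 0.30 × 0.70 = 0.42.

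Members of one family are likely to respond alike, so the two estimates may be positively correlated. At an assumed correlation of 0.5, the bivariate normal calculation gives 0.23, 0.33 and 0.29 for the same three powers. Apparent disagreement remains common.

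**3. Precision of the difference (background).** For controller adherence (PDC), Table 3 gives least detectable differences of 2.0 points for the PDL contrast and 1.0 point for the HDHP contrast. A stratum holding share s of the patients has detectable difference overall/√s. With one third children, the child-to-overall ratio should be √3 = 1.73. Table 3 gives 3.5/2.0 = 1.75 and 1.7/1.0 = 1.70, so the scaling agrees with the table.

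- Full population, PDL contrast: adults 2.0 × √1.5 = 2.45; children 2.0 × √3 = 3.46; difference √(2.45² + 3.46²) = 4.2 points.
- Full population, HDHP contrast: half of that, 2.1 points.
- Dual-asthma families: the documents give no share, so assume that a fraction f = 5% to 30% of patients belong to such families, half adults and half children, with correlation ρ = 0 to 0.5 between the two estimates. The detectable difference is overall × √(2(1 − ρ))/√(f/2).
  - PDL contrast: from 2.0 × 1/√0.15 = 5.2 (f = 30%, ρ = 0.5) to 2.0 × 1.414/√0.025 = 17.9 points (f = 5%, ρ = 0).
  - HDHP contrast: 2.6 to 8.9 points.

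A non-significant difference in this subset would therefore not show that adults and children respond alike. That is a reason to report the interval.

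**4. Are control families complete?** Controls are drawn as individuals.

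- Traditional-plan contrast: Table 3 uses 72,000 controls, and Study Population estimates 910,000 traditional-plan patients. 72,000/910,000 = 7.9%, so a matched control adult's child with asthma need not have been drawn.
- PDL contrast: 16,888 controls from about 18,000 patients in HSA-HDHPs without PDLs, taking that figure as the pool. 16,888/18,000 = 94%, so incomplete families matter much less.

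**The case against.** The strongest reply is that the test is already in the plan. The adult/child three-way term is specified one paragraph earlier for both plan contrasts, Aim 3 inherits the earlier modelling strategies, and the Aim 2 analysis section names GEE and GLMM to handle correlation among members of a family. On this reading the subset is simply a restriction of an analysis that includes the interaction.

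Much of that stands. It rules out saying that the plan has no formal adult-versus-child test, or that it ignores family correlation. A reader might also infer that the within-family analysis cannot show a differential effect. That is too strong, since a difference and its interval could be formed from the two stratum estimates if their covariance is handled. But the carry-over clause is general, and one of the two aims it cites is the interview study. The specific sentence says how the question will be answered, and an analyst following it would not fit the interaction.

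A second tempting inference is that individual matching invalidates the comparison because Table 2 codes adult/child status ("Age 18-64 vs. age 4-17") as a predictor and stratifier but not as a matching variable. The documents do not support this. Age on the index date is a matching variable in Table 2, and the text puts family-level covariates into the individual match. A propensity caliper does not force adults to be matched to adults, but the planned models are covariate-adjusted GEE, GLMM and difference-in-differences (DiD) models. Matched sets of mixed age are not shown to bias them. What remains is narrower: the plan does not say whether both family members must be in the analysed sample.

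Finally, the discordance figures apply to any pair of separate tests, and the plan does not say that it will compare p-values. That is fair, but the plan does not say what else it would do.

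**Conclusion.** The point holds in limited form. In the dual-asthma families, the stated method yields two plan effects and leaves unestimated the difference that the analysis sets out to assess. The existing interaction is written for the full Aim 3 population and is not stated to apply here.

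The illustrative size is a 32% chance of a spurious split between strata at 80% power each and 50% at 50% power each. This assumes equal true effects, equal power and independent estimates; positive correlation lowers it. The actual rate cannot be computed, because the subset's size and power are not given. The detectable differences worked out for the subset rest on an assumed share of patients and an assumed correlation.

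The documents do not show that individual matching biases the result. The analysis is secondary, so the change is worth making but does not threaten the study's main comparisons.

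**What to change.** Amend the last paragraph of Aim 3 as follows:

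1. In the dual-asthma families, fit the insurance type by study period by adult/child interaction for each plan contrast, with clustering by family, using the GEE or GLMM approach already named for Aim 2.
2. Report the adult-minus-child difference in the DiD effect, with its confidence interval, as the result. Keep the separate strata as description, and do not infer a differential effect from one stratum being significant and the other not.
3. In both arms, restrict the analysis to families whose adult and child are both in the analysed sample. Report how many such families there are, by arm and contrast.

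The cost is a change of wording and one added model term per contrast, with no new data. The restriction will lose some control families, mainly in the traditional-plan contrast.

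Whole-family matching or family fixed effects could be added as a sensitivity analysis but are not required. Tighter matching may be costly in the PDL contrast, where 16,888 controls are already needed from about 18,000 patients.
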